Protocol study and Statistical analysis plan

Effect of Parenting Training on Quality of Life and Parenting in Parents Who Have Children with Intellectual Disabilities

20 December 2024

Design

This study used a quasi-experimental design, which was conducted based on a pretest-posttest control group.

Samples

One hundred and forty-one mothers with ID children attending special schools in East Java, Indonesia, were recruited and divided into intervention (N=71) and control group (N = 70) according to a special school using a convenience sampling method. We estimated that a minimum of 60 participants in each group would be required using the G.power 3.1.9.7 application, with an effect size of 0.335, and a power of the test $(1-\beta) = 80\%$. The inclusion criteria were

- having a child aged 7-18 years who has mild and moderate intellectual disabilities
- living in the same house as a child with intellectual disabilities,
- being able to communicate fluently

The exclusion criteria were

- having disabilities
- having a child with intellectual disabilities who has a chronic disease
- having a child with intellectual disabilities and other disabilities

Instrument

Parenting quality was evaluated using the Parenting Sense of Competence (PSOC) developed by Gibaud-Wallston and Wandersman, adapted from Johnston and Marsh (Cronbach Alpha=0.79) (Johnston & Mash, 1989). Quality of life was evaluated using the World Health Organization Quality of Life (WHOQOL-BREF) (Cronbach Alpha= 0.66-0.8) developed by the WHO (Group, 1994). The WHOQOL-BREF consists of four domains (physical health, psychological, social relationships, and environment) with 26 questions. The total score for each domain is transformed to a scale of 0-100 according to the scoring guidelines. The PSOC consists of the domains of satisfaction and self-efficacy with parenting, which are assessed with 16 questions, with a satisfaction score ranging from 9 to 54 and a self-efficacy score from 7 to 42.

Intervention

The control and intervention groups were given a parenting guidebook for children with ID. The intervention group received approximately three hours of parenting training once a week for 5 weeks. The intervention group received parenting training focused on understanding children with ID in the first week, practical parenting skills in the second week, and how to provide emotional support and regulate parental emotions in the third week. Knowledge and skills were reinforced in the fourth and fifth weeks. The intervention group received training in small groups, each consisting of only 10 participants. The training involved experts in mental health counseling, pediatric nurses, special school teachers, and a motivator.

Data Collection

The PSOC and WHOQOL scores were measured by a researcher who was not blinded to the study from January to August 2025 at the school.

Data analysis:

SPSS version 23 was used to analyze the data. Categorical variables were reported as frequencies and percentages. Continuous variables were reported as median and standard deviation (SD). The Kolmogorov-Smirnov test was used to confirm normal distribution. The Wilcoxon and Mann-Whitney U tests were used for continuous variables with non-normal distributions, as well as the Chi-squared test for qualitative variables. The Wilcoxon and Mann-Whitney U tests were used for continuous variables with non-normal distributions. A p-value of less than 0.05 was considered statistically significant. The point-biserial correlation test was used to evaluate the effect size. SPSS version 23 was used to analyze the data. Categorical variables were reported as frequencies and percentages. Continuous variables were reported as median and standard deviation (SD). The Kolmogorov-Smirnov test was used to confirm normal distribution. The Wilcoxon and Mann-Whitney U tests were used for continuous variables with non-normal distributions, as well as the Chi-squared test for qualitative variables. The Wilcoxon and Mann-Whitney U tests were used for continuous variables with non-normal distributions. A p-value of less than 0.05 was considered statistically significant. The point-biserial correlation test was used to evaluate the effect size.

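### Arm appears to be set by school, but the between-group test and the 60-per-group sample size treat mothers as independent, so a positive school correlation pushes type I error above 5% by an amount the documents do not fix

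*Combined protocol and SAP*

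**What the plan says.** The Design section reads: "This study used a quasi-experimental design, which was conducted based on a pretest-posttest control group". In Samples, the 141 mothers "were recruited and divided into intervention (N=71) and control group (N = 70) according to a special school using a convenience sampling method". The wording is loose, but allocation by school is its natural meaning. The number of schools, and of mothers per school, is not given for either arm.

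The sample-size sentence in the same section states that "a minimum of 60 participants in each group would be required using the G.power 3.1.9.7 application, with an effect size of 0.335", with 80% power. It names no test, sidedness, ICC, design effect or number of schools.

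The Intervention section adds a second grouping, in one arm only: "The intervention group received training in small groups, each consisting of only 10 participants". It does not say how these groups were formed or whether they coincide with schools.

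For the scores, the Data analysis section says "The Wilcoxon and Mann-Whitney U tests were used for continuous variables with non-normal distributions", with a 0.05 significance threshold and a point-biserial correlation as effect size. That paragraph is printed twice, and neither copy mentions school. It does not say whether the Mann-Whitney test compares post-test scores or changes.

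**The concern.** The Mann-Whitney test takes the 141 mothers as independent observations. When whole schools belong to one arm, anything that mothers at a school share (teachers, catchment, local services, who agreed to take part) enters the difference between arms directly. A test that ignores this understates the variance of that difference and gives p-values that are too small.

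Every between-group p-value on the PSOC and WHOQOL-BREF scores is exposed, and any claim that the training works rests on these. The within-arm Wilcoxon tests ignore the same clustering. The 60-per-group calculation has the same gap, because its 80% power also presumes independent mothers.

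**Working it through.** **Inputs from the documents.** 71 and 70 mothers (70.5 per arm on average); training groups of 10; 0.05 threshold; 60 per group; effect size 0.335; power 80%.

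**Assumed, because the documents do not give them.** Number of schools per arm; school ICC; two-sided testing; correlations over time.

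**1. The plan's own figure.** A one-sided 5% matched-pairs Wilcoxon calculation reproduces 60. The effective n is 60 × 3/π = 57.3, the noncentrality is 0.335 × √57.3 = 2.54, and power is 80.5%. The two-sided version needs 76. That reading is inferred, since the plan names no test. This calculation, like every variant tried, treats mothers as independent.

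**2. Type I error on post-test scores.** With k equal schools per arm, m = 70.5/k, the design effect is DE = 1 + (m − 1) × ICC, and the true error of a nominal 5% test is about 2 × [1 − Φ(1.96/√DE)]. At ICC 0.05:

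| Schools per arm | m | DE | Formula | Simulated Mann-Whitney |
|---|---|---|---|---|
| 20 | 3.5 | 1.13 | 6.5% | about 6% |
| 7 | 10.1 | 1.45 | 10.4% | about 10% |
| 3 | 23.5 | 2.12 | 17.9% | about 18% |
| 2 | 35.25 | 2.71 | 23.4% | about 23% |

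The simulations used 71 against 70 mothers and 20,000 null trials per cell. At ICC 0 the error stays at about 5%. Other assumed ICCs (0.01 / 0.02 / 0.10) give 6.0 / 6.8 / 15.4% with 7 schools per arm, 7.3 / 9.8 / 27.5% with 3, and 9.0 / 13.0 / 34.8% with 2. With 3 schools against 7, ICC 0.05 gives 14.0%. No rate is given for one school per arm, because that is confounding and not a repairable test error.

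**3. If changes are compared.** Let r_s be the correlation of school effects over time and r_m that of mothers' scores within school. With equal variances at both visits, the ICC of the change is ICC(1 − r_s) / [ICC(1 − r_s) + (1 − ICC)(1 − r_m)]. Take ICC 0.05 and r_m = 0.5:

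- r_s = 0.8: 0.010/(0.010 + 0.475) = 0.021. Error is 7.5% with 7 schools per arm, 10.4% with 3 and 13.0% with 2.
- r_s = 0.9: 0.005/(0.005 + 0.475) = 0.010. Error is 6.1%, 7.4% and 9.1%.
- r_s = 1.0: the ICC is 0 and error is about 5% throughout.

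Changes therefore help when school effects are more stable over time than mothers' own scores.

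**4. Training groups alone.** With groups of 10 in one arm and no school effect, the variance ratio is (1 + 1 + 9 × ICC)/2, which is 1.225 at ICC 0.05. The error is then about 7.7%. This applies only if the groups differ at the outset or the training effect varies between groups. If training affects nobody and groups were formed without regard to outcome, delivery in groups adds nothing.

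**5. Power of the baseline-adjusted school-level test.** Take ICC 0.05, r_m = 0.5, r_s = 0.8 and total SD 1, and adjust with slope 0.5. The school variance is 0.05 × (1 + 0.25 − 0.8) = 0.0225 and the mother variance is 0.95 × 0.75 = 0.7125. The standard error is √[2(0.0225 + 0.7125/m)/k], with 2k − 2 degrees of freedom. For a difference of 0.5 SD:

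- 7 schools per arm: SE 0.163, power 80% by formula, about 81% by simulation.
- 3 per arm: SE 0.188, power 53% and about 51%.
- 2 per arm: SE 0.207, power 29% and about 29%.

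Without baseline adjustment the same test has 62%, 35% and 19%. An unadjusted t-test on independent mothers would have 84%.

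**The case against.** The strongest reply is that nothing in the documents shows a positive ICC. It could be near zero, there could be many small schools, or the comparison could be of changes in which stable school effects cancel. All of that is possible, and it limits what can be said about size. It does not rescue the plan, which neither commits to changes nor gives a reason to take the ICC as zero.

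A second reply is that a quasi-experimental study makes no claim to randomised inference. But lack of randomisation adds confounding; it does not make mothers at one school independent.

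A third is that rank tests were chosen for non-normal scores, and the remedy brings back normal-theory methods on bounded scales. This has some weight. School means are averages and so nearer to normal, but the mixed model was checked only at ICC 0.05 to 0.10, where its error was 3.1% to 4.8%.

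A reader might infer more than the documents support:

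- **That the false-positive rate is known to be several times 5%.** It is not; with 20 schools per arm the assumed case gives about 6%.
- **That there was one school per arm.** The text does not exclude this, but does not say it.
- **That the sample size was calculated on 141 mothers.** It was 60 per group; 141 is the number recruited.
- **That respecting school destroys the power.** The 62%, 35% and 19% figures hold only without baseline adjustment.

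**Conclusion.** The concern holds in conditional form. On the natural reading of Samples, arm is set by school, and neither the between-group test nor the sample size allows for it. If the compared outcome has a positive school ICC, with more than one mother per school and schools viewed as random draws, between-group type I error exceeds 5%. The direction follows from the design; the amount cannot be determined from the documents. At an assumed ICC of 0.05 on post-test scores it runs from about 6% (20 schools per arm) to about 23% (2 per arm).

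With a single school in either arm, the issue is no longer an inflated test but an effect of training that cannot be separated from an effect of school. In every case, the convenience choice of schools leaves confounding that no cluster adjustment removes.

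This should be put right before between-group p-values are relied on. Whether 0.335 is a suitable effect size for comparing the two groups is a separate sample-size question.

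**What to change.** 1. State the number of schools, and of mothers per school, in each arm, and whether post-test scores or changes are compared.
2. Replace the individual-level Mann-Whitney test as the between-group analysis by a baseline-adjusted analysis chosen on the smaller arm's school count:
   - five or more schools: a linear mixed model of post-test score on arm and baseline score, with a random intercept for school and small-sample degrees of freedom;
   - two to four: a pooled t-test on school mean baseline-adjusted scores (simulated size 3.9% to 5.5% for equal counts of 2 to 4; conservative when counts are unequal);
   - one school in either arm: describe only, with no inferential claim of a training effect.
3. Treat the within-arm Wilcoxon tests as descriptive.
4. Say in Samples that the 60 per group and 80% power assume independent mothers, and so do not hold for allocation by school if the ICC is positive.
5. Label the result post hoc if outcomes have already been seen, and state that adjustment does not remove confounding from the convenience choice of schools.

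**Cost.** Only the analysis wording changes, with no new mothers or visits, provided school membership was recorded. The documents do not confirm this, though scores were measured "from January to August 2025 at the school". The sponsor should check that SPSS 23, the named software, offers the chosen degrees-of-freedom method. Intervals usually widen. Under the assumptions in the power calculation above, a difference of 0.5 SD is detected with about 81%, 51% and 29% power with 7, 3 and 2 schools per arm, against 84% for an unadjusted test on independent mothers. Baseline adjustment therefore recovers most of the loss with 7 schools per arm, but not with 2 or 3.

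### Arm follows special school and schools are placed by convenience, so school differences, including differences in change over time, are confounded with training; the plan neither balances nor models school

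*Combined protocol and SAP*

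**What the plan says.** The Design section is open about the type of study: "This study used a quasi-experimental design, which was conducted based on a pretest-posttest control group". The Samples section gives the assignment: mothers were "divided into intervention (N=71) and control group (N = 70) according to a special school using a convenience sampling method". It uses the plural for schools but gives no count, no school characteristics, no matching, and no reason for not randomising. Eligibility covers children aged 7 to 18 with mild or moderate disability, and nothing keeps that mix similar between arms.

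Under Intervention, both arms receive the guidebook and only one receives the five weekly sessions, delivered partly by special school teachers. Data Collection places measurement "from January to August 2025 at the school", without a pretest date. Data analysis lists Wilcoxon, Mann-Whitney and chi-squared tests and a point-biserial effect size, with no covariate and no term for school. The document is dated 20 December 2024 and describes recruitment and division in the past tense.

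**The concern.** The title asks for the effect of training. If convenience decides which schools train, the comparison mixes training with whatever made a school convenient: staff engagement, parents' involvement, or the children's age and disability mix. Some of these would show as a pretest gap. Others would show only as a different course over the following months.

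Two separate problems follow. Convenience placement can shift the expected difference between arms away from zero when training does nothing. Separately, mothers at one school resemble each other, so a test that treats 141 mothers as independent understates the uncertainty even if schools had been drawn at random. The planned analysis addresses neither.

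**Working it through.** **The plan's own figure.** The only calculated figure in Samples is 60 per group, "with an effect size of 0.335" and 80% power. It reproduces as a one-sided signed-rank test at alpha 0.05 (paired t-test n = 56.47; 56.47 × π/3 = 59.1, rounded up to 60). Sidedness and alpha are inferred. This is a within-group calculation with no allowance for school, so it does not bear on allocation.

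**Inputs from the documents.** 71 and 70 mothers; two-sided 0.05 taken from Data analysis (sidedness assumed).

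**Assumed inputs.** k = 2, 4 or 7 equal-sized schools per arm. ICC of change 0.05 or 0.10, with total SD of change = 1. Correlation ρ = 0.5 between a school's willingness to train and its mean change. The k most willing of 2k schools train. No training effect.

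**Mean bias.** Bias = ρ × √ICC × g, where g is the expected gap in willingness between the upper and lower halves of 2k standard normal values: 1.33, 1.45 and 1.51 for k = 2, 4 and 7.

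- Smallest: 0.5 × √0.05 × 1.33 = 0.15 SD.
- Largest: 0.5 × √0.10 × 1.51 = 0.24 SD.
- With ρ = 0.8: 0.24 to 0.38 SD.
- With ρ = 0.5 and ICC 0.01: about 0.07 SD.
- With schools randomised: zero on average.

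**False rejection when mothers are treated as independent.** With randomised schools the approximation is 2 × [1 − Φ(1.96/√DE)], where DE = 1 + (70.5/k − 1) × ICC. For k = 2 and ICC 0.05, DE = 1 + 34.25 × 0.05 = 2.71 and the rate is 23%. For k = 7 and ICC 0.05, DE = 1.45 and the rate is 10%. A simulation of both kinds of allocation (20,000 trials per cell, two-sample t-test on change standing in for the rank test, Monte Carlo error at most 0.35 points) gave:

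| Schools per arm | ICC | Mean bias, ρ = 0.5 | Rejects, randomised | Rejects, convenience |
|---|---|---|---|---|
| 2 | 0.05 | 0.15 | 23.9% | 28.5% |
| 2 | 0.10 | 0.21 | 36.5% | 41.5% |
| 4 | 0.05 | 0.16 | 15.0% | 23.2% |
| 4 | 0.10 | 0.23 | 23.4% | 36.2% |
| 7 | 0.05 | 0.17 | 10.7% | 21.5% |
| 7 | 0.10 | 0.24 | 15.8% | 35.4% |

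The excess over 5% therefore has two parts. With 2 schools per arm and ICC 0.05, ignored clustering adds 18.9 points (23.9 − 5) and convenience a further 4.6 (28.5 − 23.9). With 7 per arm the order reverses: 5.7 and 10.8.

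**What a random draw of schools can support.** The smallest two-sided permutation p is 2 divided by the number of equally likely allocations.

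- 2 v 2: 2/6 = 0.33.
- 3 v 3: 2/20 = 0.10.
- 4 v 4, unrestricted: 2/70 = 0.029.
- Four pairs: 2/16 = 0.125.
- Six pairs: 2/64 = 0.03.

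A school-level permutation test can reach p < 0.05 only with more than 40 allowed allocations (2/0.05 = 40).

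**The case against.** The strongest reply is that the plan discloses all this: it calls itself quasi-experimental and reports convenience division by school. That stands as disclosure. It does not remove the confounding, and nothing in the text limits the causal claim in the title. It is also fair that the document has no conclusions section, so the wording at issue is so far only the title's, and that the sentence on division is loose: convenience is grammatically attached to sampling, and whole-school assignment is the natural reading rather than an explicit statement.

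Several stronger readings are tempting and not supported:

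- A reader might infer that schools could have been randomised at almost no cost before a January pretest. The documents say nothing about cost, consent or feasibility, give only a January to August window, and report the division as done. Whether assignment was still open is unknown.
- A reader might divide a bias of 0.15 to 0.24 SD by √(1/71 + 1/70) = 0.168 and conclude that convenience alone lifts the error rate from 5% to about 14-30%. That standard error ignores the ICC from which the bias was derived. The proper comparison is with randomised schools tested in the same way.
- A reader might say that no baseline adjustment helps. Pretest adjustment would remove part of the stable differences; what it cannot reach is a difference in how schools change.
- The idea that schools agreed to host training is a guess, as no training venue is stated. Willingness is one possible mechanism among several.

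Randomisation also does little if there are very few schools. With one school per arm, school and training remain inseparable however the arm is chosen.

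**Conclusion.** The point holds in a limited form. Arm follows school, schools are not placed at random, and neither design nor analysis deals with school, so the planned comparison cannot by itself be read as the effect of training.

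Under the stated assumptions the mean bias is about 0.15 to 0.24 SD. That is roughly 45-70% of the planning effect of 0.335, if that value is an SD difference (its metric is not given). Mother-level tests would reject a true null in about 21-42% of trials, against about 11-36% with randomised schools and clustering still ignored. The number of schools, the ICC and the correlation are all assumed, and the bias shrinks to about 0.07 SD at ICC 0.01. The direction of any real bias is not known. A random draw of schools would deal with the bias on average but not with the clustering, so it is not sufficient alone.

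**What to change.** In Samples, state the number of schools, the number of mothers from each, and how each school was assigned.

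**If assignment is still open and enough schools will accept either arm:**

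- Assign schools by a recorded random draw, made before any pretest by someone not involved in recruitment, and balanced on school size, disability level and age mix. Describe the study as cluster-randomised.
- With few schools, restrict an unpaired draw instead of pairing, and keep more than 40 allowed allocations so that p < 0.05 can be reached.
- In Data analysis, compare arms with a method that accounts for school and adjusts for the pretest.

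**If assignment is closed, or there are too few schools:** account for school as far as the number allows, adjust for the pretest, and word the conclusion as a difference between schools that did and did not receive training, not as the effect of training.

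**Cost.** The first route needs an amendment and a draw. Schools lose the choice of arm and some may drop out. Accounting for school also widens confidence intervals: by the design effects above, standard errors grow by a factor of about 1.2 (√1.45; 7 per arm, ICC 0.05) to 2.1 (√4.43; 2 per arm, ICC 0.10), before any gain from the pretest. Whether the present number of mothers would then suffice is not established. The second route needs no new data; its price is a more cautious conclusion and, where school is modelled, the same wider intervals.

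### The minimum of 60 per group does not follow from effect size 0.335 and 80% power for an unadjusted comparison of the two groups, whether 0.335 is read as d, f or r

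*Combined protocol and SAP*

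**What the plan says.** The Samples section gives the plan's only power statement: "a minimum of 60 participants in each group would be required using the G.power 3.1.9.7 application, with an effect size of 0.335", with power of 80%. It records 71 mothers in the intervention group and 70 in the control group. It does not name the test, say whether 0.335 is a d, f, r or paired effect size, or give sidedness, alpha, a dropout allowance or a pre-post correlation.

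The other sections supply some context:

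- **Design:** a quasi-experimental study, "which was conducted based on a pretest-posttest control group".
- **Intervention:** "The control and intervention groups were given a parenting guidebook for children with ID", so the arms differ only in the training.
- **Data analysis:** "The Wilcoxon and Mann-Whitney U tests were used for continuous variables with non-normal distributions"; "A p-value of less than 0.05 was considered statistically significant"; and "The point-biserial correlation test was used to evaluate the effect size". Nothing links the point-biserial correlation to the 0.335, and no baseline-adjusted between-group analysis is described.

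**The concern.** Because both arms receive the guidebook, a pre-post change within the trained arm cannot isolate the effect of training. That effect rests on comparing the two arms, so this is the comparison the sample size should support.

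The three stated figures (60 per group, 0.335, 80%) do not agree for that comparison on the usual readings. A reader cannot tell whether its power at 60 per group is about 43% or about 97%. If 0.335 is a d, a null between-group result would be wrongly read as coming from an adequately powered study.

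**Working it through.** **Inputs.** From Samples: effect size 0.335, power 80%, 60 per group planned, 71 and 70 recruited. From Data analysis: the 0.05 threshold, assumed here to apply to the sample size as well. Sidedness is not stated, so both are shown. Clustering by school and by training group is ignored throughout.

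**Formulas.** As a first approximation, n per group = 2(z₁₋α + z₁₋β)² / d², with z₁₋α/₂ in place of z₁₋α for a two-sided test. The tabulated values use the noncentral t. Mann-Whitney and signed-rank figures multiply n by the asymptotic relative efficiency for a normal parent, 3/π = 0.955.

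**Conversions to d (equal groups).**

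- As d: 0.335.
- As f: d = 2f = 0.67.
- As r: d = 2r/√(1 − r²) = 0.67/√(1 − 0.1122) = 0.711.

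**Attempt to reproduce 60 for the group comparison.** With d = 0.335 two-sided, 2(1.960 + 0.842)²/0.335² = 139.9, or 140 per group. The noncentral t gives 141, and allowing for the rank test gives 148. The full set, n per group for 80% power:

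| 0.335 read as | Two-sided t / Mann-Whitney | One-sided t / Mann-Whitney |
|---|---|---|
| d | 141 / 148 | 111 / 117 |
| f | 36 / 38 | 29 / 30 |
| r | 33 / 34 | 26 / 27 |

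The point-biserial correlation model gives a total of 65 two-sided or 51 one-sided, in line with the last row. Changing the parent distribution for the rank test does not help: across distributions and sidedness, d needs 74 to 164 per group, f 19 to 42 and r 17 to 38.

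**Power of the two-sided Mann-Whitney test.** Simulated values (20,000 runs) are in brackets.

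| 0.335 read as | 60 / 60 | 71 / 70 |
|---|---|---|
| d | 0.428 (0.426) | 0.488 (0.483) |
| f | 0.945 (0.945) | 0.971 (0.972) |
| r | 0.965 (0.966) | 0.984 (0.983) |

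One-sided with d, the values are 0.555 and 0.614. The smallest d detectable with 80% power, two-sided, is 0.528 at 60/60 and 0.486 at 71/70.

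**What does give 60.** A one-sided Wilcoxon signed-rank test on paired differences with dz = 0.335 starts from (1.645 + 0.842)²/0.335² = 55.1 pairs. The noncentral t raises this to 57, and the rank-test efficiency raises it to 60. Power is 0.805 at 60 and 0.799 at 59, so 60 is exactly the minimum. Two-sided, the same test needs 76.

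**Baseline adjustment.** Adjusting for the pretest turns d into d/√(1 − ρ²), where ρ is the pre-post correlation. To reach 80% at 60/60 with d = 0.335, ρ must be 0.773 two-sided or 0.697 one-sided. The plan gives no ρ, so the range is shown for assumed values (two-sided, rank-test efficiency applied):

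| Assumed ρ | 60 / 60 | 71 / 70 |
|---|---|---|
| 0.5 | 0.537 | 0.606 |
| 0.7 | 0.702 | 0.771 |
| 0.8 | 0.842 | 0.895 |

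**Other routes.** Reading 0.335 as f with 95% power gives 59 per group, but the plan states 80%. Starting from 36 (f) or 33 (r) and inflating for dropout would need a loss of 1 − 36/60 = 40% or 1 − 33/60 = 45% to reach 60, and no dropout allowance is stated.

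**The case against.** The strongest reply is that the sentence is under-specified rather than wrong. It does not say which comparison it sizes. Wilcoxon is among the planned tests, the design is pretest-posttest, and the three numbers fit exactly for a one-sided signed-rank test. Moreover, a shortage of power appears only if 0.335 is a d. The one effect-size measure the plan names is a correlation, and on the r or f reading 60 per group is more than enough. Recruitment also exceeded 60, and correcting the sentence changes no estimate or p-value.

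Part of this stands. The documents do not show which calculation was run, and the signed-rank origin is an inference. On the f and r readings the fault is that 60 is not the minimum; adequacy is not in doubt.

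The rest does not remove the problem. The plan offers 60 in each group as the minimum for a controlled design, and the unadjusted comparison of the groups does not return that figure on any of the three metrics. If the signed-rank explanation is right, the study was sized on a contrast that ignores the control arm. Exceeding 60 does not settle the matter either, because 71 and 70 still give only 49% power if 0.335 is a d.

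**Conclusion.** The concern holds. For an unadjusted intervention-versus-control comparison at alpha 0.05, the stated 60 per group, 0.335 and 80% are mutually inconsistent: 60 is less than half the two-sided requirement if 0.335 is d (141 to 148) and well over the minimum if it is f (36 to 38) or r (33 to 34). At 71 and 70, two-sided Mann-Whitney power is 49%, 97% or 98% respectively.

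These figures assume that the 0.05 threshold governs the sample size, that a normal parent is adequate for the rank-test efficiency, and that mothers are independent. Allocation by school and training in groups of 10 are not allowed for. The harm to interpretation is conditional on 0.335 being a d, which the plan neither states nor rules out. The sentence must be corrected because it is the plan's only power claim and cannot be relied on for the comparison that matters.

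**What to change.** First check the original G*Power settings for the test, metric, tails and alpha. Then replace the sample-size sentence with a between-group statement that names all four. Wording that is correct whatever 0.335 originally meant:

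> For the unadjusted two-sided Mann-Whitney comparison at alpha 0.05 with 71 versus 70 mothers, the study has 80% power for a standardised difference d of about 0.49 and about 49% power for d = 0.335, before any allowance for clustering.

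- If 0.335 was an r or an f, say so and give the minimum it implies (about 33 to 34 or 36 to 38 per group, two-sided). The clause on d = 0.335 can then be dropped.
- Remove the claim of 60 per group at 80%. If the authors confirm its origin, label it as a one-sided within-arm signed-rank calculation.
- Do not attach the 49% to a baseline-adjusted analysis. If one is adopted, state the assumed pre-post correlation and recompute: about 61% to 90% at 71/70 for correlations of 0.5 to 0.8.

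The cost is one paragraph and a look at the saved settings, with no extra enrolment. The stated power becomes less favourable if 0.335 is a d.

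### An unblinded researcher measures both self-reported outcomes, how the forms are completed is not stated, and no safeguard against expectation bias is described

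*Combined protocol and SAP*

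**What the plan says.** Under Data Collection the combined protocol and SAP has one sentence on outcome assessment. It says that both sets of scores were "measured by a researcher who was not blinded to the study", at the school, between January and August 2025.

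The Instrument section describes the two outcome measures:
- "The PSOC consists of the domains of satisfaction and self-efficacy with parenting, which are assessed with 16 questions".
- "The WHOQOL-BREF consists of four domains (physical health, psychological, social relationships, and environment) with 26 questions".

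Under Samples, allocation is by special school, with 71 mothers in the intervention arm and 70 in the control arm. The only related ability required of a mother is "being able to communicate fluently"; there is no reading criterion.

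Under Intervention, both arms receive a guidebook. Only the intervention arm attends training, about three hours weekly for five weeks. The people involved in the training include "special school teachers, and a motivator".

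The document does not say who holds the pen, whether the researcher also trains, who else is in the room, how forms are labelled, or whether scoring and analysis are masked.

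**The concern.** Every outcome is a mother's judgement of her own life or parenting, and no objective measure is planned against which to check it. The PSOC asks about satisfaction and self-efficacy in parenting, which is close to what the training teaches. If a mother gives her answers to a member of the study team who knows her arm, two things can move the score without any change in her parenting or quality of life: the way the items are put to her, and her wish to give the answer the team hopes for.

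The second pressure is plausibly greater in the intervention arm, which has just had extended contact with the training team. Control mothers also received study material, so theirs is likely less rather than absent. A shift in favour of the training would then be read as a benefit of it.

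**Working it through.** **1. What the text establishes.** Both outcomes are measured by someone who knows the arm. Masking the assessor would be hard even if intended: allocation is by school and measurement is at the school, so the site can reveal the arm.

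**2. What the text leaves open.** "measured by a researcher" fits two procedures. In one, the researcher reads the items and records the answers. In the other, the researcher hands out, collects and scores forms that the mothers filled in. The route for researcher-induced bias is wide in the first and narrow in the second.

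**3. Difference in contact.** Intervention: 3 hours × 5 weeks = 15 hours. Control: guidebook, no training sessions.

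**4. Whether the analysis could remove the bias.** A pre-test is planned. A shift that arises after training is absent at pre-test and present at post-test, so it stays in both the post-test score and the change score, aligned with arm. The Wilcoxon test, the Mann-Whitney test and the point-biserial correlation all count it as effect.

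**5. Size (illustration only).** The documents give no bias figure, so there is none to reproduce. Inputs: n₁ = 71 and n₂ = 70 (Samples); significance level 0.05 (Data analysis), taken as two-sided because the plan does not say; a constant researcher-induced shift b in SD units (assumed); true effect zero (assumed).

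- Noncentrality: λ = b × √(n₁n₂/(n₁ + n₂)) = b × √(4970/141) = b × 5.937.
- Degrees of freedom: 71 + 70 − 2 = 139.
- Rejection rate: the probability that a noncentral t with 139 degrees of freedom and noncentrality λ falls outside the two-sided 5% critical values.

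| Assumed shift b (SD) | λ | Rejection rate |
|---|---|---|
| 0 | 0 | 5.0% |
| 0.10 | 0.594 | 9.1% |
| 0.15 | 0.891 | 14.3% |
| 0.20 | 1.187 | 21.8% |

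An observed difference of about 0.333 SD is enough for significance at these sample sizes.

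This uses a t-test, whereas the plan names Mann-Whitney for non-normal data. It treats mothers as independent although they were allocated by school, and it covers one test only.

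**6. Why the shift is not set against the planned effect of 0.335.** The plan does not state the metric of 0.335. Of the variants tried, only a one-sided matched-pairs Wilcoxon calculation (asymptotic relative efficiency 3/π) gives the stated 60 per group, with power 0.805. A two-sided two-sample t-test at 0.335 SD would need 141 per group. If 0.335 is in SDs of within-person change, dividing a between-group shift by it would mix units.

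**The case against.** The strongest reply is that the forms may already be self-completed. Nothing in Data Collection excludes it. The main remedy would then be in place, and the point would shrink to a request to say so. That stands, and it is why the conclusion is conditional.

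Second, the mothers know whether they were trained, whoever holds the form. Self-completion removes the interviewer's influence but not the mother's own expectation. The illustration assumes that the whole shift comes from the researcher; the documents offer no way to split it, so the table does not measure what the fix would gain. This also stands.

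Third, the plan discloses the lack of blinding openly. That is to its credit, but disclosure does not reduce the bias.

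Fourth, masked scoring adds little, because both questionnaires are scored by rule. This is accepted; it is a minor part of the fix.

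A reader might also infer more than the documents support:
- *That mothers could all complete the forms themselves at no staff cost.* The documents give no costs, and fluent communication is not literacy.
- *That teachers who trained the mothers were present at measurement.* Teachers took part in the training, but the plan does not place those teachers at the measuring schools or in the room.
- *That control mothers feel no pressure to please.* Less pressure is plausible; none is not shown.

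**Conclusion.** The point holds in a limited form. Two subjective outcomes are measured by an unblinded researcher, the mode of completion is unstated and no safeguard is described. If the researcher took the answers, a bias towards the intervention is plausible and the planned analysis cannot remove it.

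Its size is unknown. The rise from 5% to between 9% and 22% rests on an assumed shift of 0.1 to 0.2 SD that is entirely researcher-induced, no true effect, a two-sided t-test and independent mothers. It shows that a modest shift would matter; it does not estimate what happened or will happen. A reader might infer that a positive result would be an artefact of measurement. The documents do not support that, because they give neither the procedure nor any estimate of the bias.

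The change is worth making because it is simple and acts on a procedure the plan does describe.

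**What to change.** Change the Data Collection text to state, for both arms at pre-test and post-test:

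1. Mothers who can read complete the PSOC and WHOQOL-BREF themselves, in writing, with the same printed instructions.
2. Forms carry only a study number, and no one who delivered training is present.
3. Forms are checked for blank items before the envelope is sealed, without discussing the answers.
4. Mothers who need help have the items read from a fixed script, where possible by an existing team member who did not train them. Each use is recorded.
5. Scoring and analysis use masked arm codes.

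State in the conclusion that mothers remained unblinded, so self-report bias towards the intervention is reduced, not removed.

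If data have already been collected, three parts remain open: report how the forms were completed and by whom scored, mask the arm codes for any scoring and analysis still to be done, and state the limitation.

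The cost is printing, envelopes and a wording change. Little or no added staff time seems likely, but that is a judgement and depends on a non-trainer being available. The downside is some more blank items, and assisted completion for some mothers, for whom interviewer influence is limited by the script but not eliminated.
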